4.1.3. Visit Windows

It is expected that all visits should occur according to the protocol schedule. No assessment windows are defined for visit based assessments. Detail of premature withdrawal and unscheduled visit assignments is found in Section [6.2.5](#).

4.1.4. Study Completion

The study is designed to collect data after premature discontinuation of treatment. Participants are considered to have completed the study if they meet the following criteria regardless of premature discontinuation of interventional product.

Participants enrolled for 52 Weeks

A participant is considered to have completed the study if they continue to participate in the study until the Exit Visit at Week 52.

Participants enrolled beyond 52 Weeks (or re consented to continue beyond 52 Weeks)

A participant is considered to have completed the study if they continue to participate in the study until the earlier of:

The Exit Visit at Week 104

OR

A scheduled visit that is on or immediately before the date of the Exit Visit at Week 52 of the last participant to have been randomized into the study.

By study design, the duration of study will vary for the participants enrolled beyond 52 Weeks (or re consented to continue beyond 52 Weeks).

4.2. Primary Endpoint Analyses

4.2.1. Definition of Primary Endpoint/Estimand

The primary endpoint is the annualized rate of moderate or severe exacerbations occurring during the study period. The study is designed to continue collecting exacerbation data for participants who have prematurely discontinued from IP and remain in the study.

For analysis, moderate exacerbations are defined as clinically significant exacerbations that require treatment with oral/systemic corticosteroids and/or antibiotics. Severe exacerbations are defined per protocol as clinically significant exacerbations that require in-patient hospitalization (i.e., ≥ 24 hrs.) or result in death. The study inclusion criteria required at least 2 moderate COPD exacerbations treated with systemic corticosteroids (intramuscular (IM), intravenous, or oral) with or without antibiotics or at least one severe exacerbation in the 12 months prior to Screening Visit 1.

Moderate and severe exacerbations occurring from the start of interventional product (IP) will be included in the primary analysis regardless of whether the exacerbation occurs after a participant prematurely discontinues from IP. For participants who complete the study (Section 4.1.4), all moderate/severe exacerbations occurring up to study completion will be included in the primary analysis. For participants who withdraw early from the study all moderate/severe exacerbations occurring up to the date of study withdrawal will be included in the primary analysis, these participants will be considered to have missing data from the date of study withdrawal up to their planned study completion date.

For all summaries and analyses, exacerbations occurring within 7 days of each other within a given participant will be handled as a continuation of the same exacerbation, assigned to the greatest severity.

The primary estimand is the difference between mepolizumab 100 mg SC and placebo (both added to optimized standard of care) in the annualized rate of moderate/severe exacerbations in participants with COPD experiencing frequent exacerbations and characterized by eosinophil levels, regardless of IP discontinuation/interruption or changes in background medication/starting a prohibited medication, in the absence of COVID-19 pandemic related intercurrent events.

The primary estimand is described by the following attributes:

Population: Participants with COPD experiencing frequent exacerbations and characterized by eosinophil levels

Treatment condition: Mepolizumab 100 mg SC vs. placebo (both as add-on treatment to optimized standard of care)

Variable: Number of moderate or severe exacerbations

Summary Measure: The summary measure of treatment effect will be the ratio of the frequency of exacerbations in the mepolizumab 100 mg treatment arm to the frequency in the placebo arm. Exacerbation rates will be expressed as an annualized exacerbation rate.

Intercurrent events: The anticipated intercurrent events for this trial are discontinuation of IP, interruption of 2 or more consecutive doses of IP, use of prohibited medications and change in background medication.

A treatment policy strategy will be used to handle the intercurrent events of discontinuation of IP and interruption of 2 or more consecutive doses of IP when not associated with disruptions or restrictions (e.g. lockdown measures, social distancing) imposed due to the COVID-19 pandemic, under this strategy exacerbations and time in study will be included in the analysis regardless of the intercurrent event. A hypothetical strategy will be used to handle these intercurrent events when they are known to be associated with disruptions or restrictions imposed due to the COVID-19 pandemic. Under this strategy exacerbations, and the period of time in study occurring after the intercurrent event, will be set to missing and handled as missing data.

A treatment policy strategy will be used to handle the intercurrent events of change in background therapy and use of prohibited medications.

Rationale for estimand: The use of a hypothetical strategy recognizes any effect on exacerbations due to discontinuation /interruption of 2 or more consecutive doses of IP associated with disruptions or restrictions imposed due to the COVID-19 pandemic, may not have occurred in the hypothetical scenario of the absence of the pandemic.

4.2.2. Main analytical approach

Statistical Methodology Specification

Endpoint / Variables					
Annualized rate of moderate or severe exacerbations (mITT, mITT2 and Per Protocol).					
Model Specification					

Data from previous studies show the numbers of moderate/severe exacerbations follow a negative binomial distribution. The primary analysis of the annualized rate of moderate/severe exacerbations will use a negative binomial model, including both on-treatment and, where available, off-treatment exacerbation data.
 
The analysis model will include covariates as shown below and an offset variable of \log_e (length of time in study) which reflects the period of time in the study for which exacerbation data has been recorded for inclusion in the analysis model. Missing data will be considered as missing at random (MAR).
 
 
 Fixed Categorical:	Treatment group, Geographic Region, Smoking Status	
 
 Fixed Continuous:	Baseline disease severity (as % predicted post-bronchodilator FEV₁), number of moderate/severe exacerbations in previous year ($\leq 2, 3, \geq 4$ as ordinal)	
 
 
 Participants with missing covariate information will be excluded from the analysis. 		Fixed Categorical:	Treatment group, Geographic Region, Smoking Status	Fixed Continuous:	Baseline disease severity (as % predicted post-bronchodilator FEV ₁), number of moderate/severe exacerbations in previous year ($\leq 2, 3, \geq 4$ as ordinal)
Fixed Categorical:	Treatment group, Geographic Region, Smoking Status				
Fixed Continuous:	Baseline disease severity (as % predicted post-bronchodilator FEV ₁), number of moderate/severe exacerbations in previous year ($\leq 2, 3, \geq 4$ as ordinal)				
Model Checking & Diagnostics					

 Missing data is assumed missing at random. Departures from this assumption will be tested for the primary endpoint (see Section 4.2.3). Models will be checked for issues with convergence. 					
Model Results Presentation					

 The model estimated mean annualized rate of exacerbations will be calculated using the observed marginal distributions of the study population covariates by inclusion of the OM (obsmargins) option in the LSMEANS statement of the GENMOD procedure. The estimated mean annualized rate of moderate/severe exacerbations for each treatment group and the rate ratio for mepolizumab vs. placebo with 95% confidence intervals and associated p-values will be presented in a table and associated figure. 					
Subgroup Analyses					
Separate exploratory subgroup analyses of the primary endpoint (mITT) will be carried out as detailed in Section 4.10.1.					

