2. INTRODUCTION

2.1. Study Rationale

While chronic obstructive pulmonary disease (COPD) is generally viewed as a disease driven by neutrophilic inflammation, up to 40% of COPD patients have an inflammatory pattern that includes elevated sputum eosinophils [Brightling, 2005; Saha, 2006]. In severe COPD patients, sputum eosinophils and Interleukin (IL)-5 levels are elevated to similar levels as those seen in severe asthmatics [Bafadhel, 2012a]. Notably, COPD patients with eosinophilic inflammation cannot be distinguished based on clinical features and lung function alone from those without eosinophilic inflammation [Saha, 2006]. Furthermore, increased eosinophilic inflammation in COPD has been associated with increased risk of exacerbations [Vedel-Krogh, 2016]. COPD exacerbations are characterized by periods of acute worsening of symptoms, deterioration in lung function, and decreased health-related quality of life (HRQoL) [Vogelmeier, 2017] and potentially contribute to further permanent decrements in lung function. Recent studies identified that increased eosinophilic airway inflammation occurred during COPD exacerbations [Bafadhel, 2011] and that peripheral eosinophils levels in the blood were used successfully as a surrogate marker to predict response to corticosteroid therapy [Bafadhel, 2012b; Bafadhel, 2017]. A study by Siva et al [Siva, 2007] showed that a treatment strategy that aimed to reduce sputum eosinophils in COPD showed a significant reduction in severe exacerbations compared to a treatment strategy aimed towards symptom reductions alone.

Based on the observation that airway eosinophilic inflammation is associated with COPD exacerbations [Bafadhel, 2011; Bafadhel, 2017], that a treatment regimen designed to reduce eosinophils will attenuate COPD exacerbations, and that airway levels of IL-5 and eosinophils are comparable in both severe eosinophilic asthma and in eosinophilic-phenotype of COPD, the mepolizumab COPD program was designed to study a COPD patient population meeting a blood eosinophil threshold with a history of exacerbations despite receiving inhaled corticosteroid (ICS)-based triple maintenance therapy. This clinical experience and the successful reduction of acute exacerbation of COPD (AECOPD) by IL-5 inhibition with mepolizumab [Pavord, 2017] suggests that the management of exacerbations can be tailored by therapy directed at a treatable trait.

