2.2. Background

COPD is a chronic progressive disease with rising morbidity and mortality and is currently the fourth leading cause of death in the world [WHO Report, 2008]; Lozano, 2012]. The disease course is marked by progressive deterioration in airflow and increase in AECOPD frequency that contribute to the overall disease severity [Vogelmeier, 2017]. In addition, a study by [Hurst, 2010] showed that the single best predictor of exacerbations was previous exacerbations.

AECOPD are heterogeneous in nature with respect to their inflammatory component. A study by Siva et al [Siva, 2007] showed that a treatment strategy that aimed to reduce sputum eosinophil counts in COPD showed a significant reduction in severe exacerbations compared with a treatment strategy aimed towards optimizing symptoms alone. Subsequent studies found that increased eosinophilic airway inflammation occurred during COPD exacerbations [Bafadhel, 2011] and that blood eosinophil levels were used successfully as a surrogate for sputum eosinophil levels to predict response to corticosteroid therapy [Bafadhel, 2017]. Furthermore, the 2019 GOLD report recommends the use of blood eosinophil count as a biomarker for considering treatment of COPD with inhaled corticosteroids [GOLD, 2019]. Additionally, the results from the mepolizumab COPD initial phase IIIA studies indicate that blood eosinophil levels are a useful biomarker to tailor treatment and prevent exacerbations for those COPD patients with an eosinophilic phenotype defined by the level of blood eosinophil counts [Pavord, 2017].

The [GOLD, 2019] report advocates the use of one or more long-acting inhaled bronchodilators (long acting beta2 -agonist [LABA]) or (long acting muscarinic antagonist [LAMA]) in addition to ICS for patients with more advanced disease, high blood eosinophil count and high risk of exacerbations [GOLD, 2019]

The concurrent use of these medications (i.e., ICS plus LABA plus LAMA) is often termed ‘triple inhaled maintenance therapy’ and is usually considered optimal for COPD patients at risk of exacerbations. For patients who continue to exacerbate despite the use of triple inhaled therapy (approximately 40% of patients on inhaled triple therapy), there are limited additional maintenance treatment options. Of these patients, approximately 20% have eosinophil levels ≥ 300 cells/ μL [Müllerova, 2017].

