	
investigator/site staff to encourage the participant to remain in the study for continued collection of efficacy and safety data.
 
Exacerbations reported by participants from the start of treatment up to the Exit Visit will be included in the primary analysis
 
The primary analysis of the rate of moderate/severe exacerbations will use a negative binomial model, including both on-treatment and, where available, off-treatment exacerbation data. Any remaining missing data will be considered missing at random (MAR). This model will include covariates of smoking status (current vs previous smoker), number of exacerbations in previous year, baseline disease severity (as % predicted post-bronchodilator FEV₁) and geographic region. The rate of moderate/severe exacerbations will be analysed using a negative binomial regression model.
 
Sensitivity analyses to the assumption regarding missing data will be performed using multiple imputation methods based on pattern mixture models. These sensitivity analyses will include an off-treatment imputation approach based on the off-treatment data collected from participants who continue in the study following early discontinuation of randomized treatment and a tipping point analysis. Further details will be provided in the RAP.
 
Full details of the analysis methods to be used will be provided in the RAP.

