4.2.5. Exploratory Modelling

The role of blood eosinophil counts on the effectiveness of mepolizumab with respect to the number of moderate/severe exacerbations will be investigated. The number of moderate/severe exacerbations will be predicted at each level of the screening \log_e blood eosinophil count based on a model including a screening \log_e blood eosinophil count main effect term and an interaction with treatment term.

The best fitting form of the interaction (i.e. which maximizes the likelihood function) between treatment group and screening \log_e blood eosinophil count will also be explored.

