5. SAMPLE SIZE DETERMINATION

The primary analysis is based on comparing the annualized rate of moderate/severe exacerbations in participants treated with mepolizumab 100 mg SC vs. placebo.

The null hypotheses used to test the superiority of mepolizumab 100 mg compared to placebo will be:

$$H_0: \mu_i = \mu_p$$

where μ_i is the annualized exacerbation rate on the mepolizumab 100 mg SC arm and μ_p is the annualized exacerbation rate on the placebo arm.

The (one-sided) alternative hypothesis is that the annualized exacerbation rate is lower on the mepolizumab arm:

$$H_a: \mu_i < \mu_p$$

The estimated annualized rate of moderate/severe exacerbations in the placebo arm was 1.7 exacerbations (based on exacerbation data observed from studies MEA117113 and MEA117106 [High Stratum], which were conducted prior to the COVID-19 pandemic).

Based on a true population reduction of 23% in the annualized rate of moderate/severe exacerbations following treatment with mepolizumab 100 mg SC compared to placebo, it was estimated that 400 participants per arm (800 participants in total) are required to provide 90% power to detect a statistically significant reduction at the 2-sided 5% level of significance. The smallest observed effect which is predicted to result in a statistically significant difference between mepolizumab 100 mg SC compared to placebo is 15%.

To account for the loss of patient years' data from participants who withdraw early from the trial and no longer provide any data (on- or off-treatment), the sample size includes an additional 44 patients to account for approximately 5.5% of patient-years data being missing, this being the level of missing data encountered in study MEA117113.

The sample size estimate is based on the number of moderate/severe exacerbations per year following a negative binomial distribution [Keene, 2007]. The estimate of 1.7 moderate/severe exacerbations per year in the placebo arm and of 0.55 for the dispersion parameter are based on data observed from studies MEA117113 and MEA117106 (High Stratum). Overall, in this study, a total of approximately 800 participants will be randomized with a randomization ratio of 1:1 placebo: mepolizumab 100 mg SC.

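### The primary rate model does not adjust for the screening eosinophil count, a baseline variable already collected; adding it would bring a small gain in precision.

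*SAP*

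**What the plan says.** SAP 4.2.2 specifies a negative binomial model with a log-time offset. The categorical terms are "Treatment group, Geographic Region, Smoking Status". The continuous terms are percent predicted post-bronchodilator FEV1 and the prior-year moderate/severe exacerbation count, scored in three ordered levels. Protocol 9.4.1 names the same covariates. Neither list contains eosinophils. SAP 4.3.5.2 (exacerbations with ED visit or hospitalization) and 4.4.2.2 (severe exacerbations and exacerbations by treatment type) take their model from 4.2.2.

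The count appears elsewhere:
- Protocol 2.1 says that "increased eosinophilic inflammation in COPD has been associated with increased risk of exacerbations".
- The schedule in Protocol 1.3.1 makes the Visit 0 hematology sample mandatory, and at least 300 cells/µL is needed to go on to Visit 1.
- SAP 4.1.2 defines the screening value, with a fallback if it is missing, and uses it as the baseline value.
- SAP 4.2.5 announces an exploratory analysis: "The role of blood eosinophil counts on the effectiveness of mepolizumab with respect to the number of moderate/severe exacerbations will be investigated". Its model has the log screening count as a main effect and in interaction with treatment.
- SAP 4.7.2 adjusts the pharmacodynamic model for the log baseline count.
- SAP 4.10.1 has a subgroup split at 0.5 GI/L.

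**The concern.** In a negative binomial model, differences between patients that the covariates do not explain go into the dispersion, and dispersion widens the interval for the rate ratio. A baseline variable related to the event rate can remove part of it. The count is measured before randomization, should be present for almost everyone, and needs no new data. Protocol 6.3 describes separate randomization schedules by country and mentions no eosinophil stratification, so a chance imbalance in this marker would go unadjusted in the primary estimate.

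The exploratory model in 4.2.5 does not repair this, because its precision does not carry over to the primary rate ratio. What is at stake is efficiency, in a trial whose protocol was amended because exacerbations were fewer than planned.

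**Working it through.** **Inputs from SAP section 5:** placebo rate 1.7 per year; "Based on a true population reduction of 23% in the annualized rate of moderate/severe exacerbations", so the rate ratio is 0.77 and the mepolizumab rate is 1.7 × 0.77 = 1.309; dispersion k = 0.55; one year of follow-up; two-sided 5% level; 756 evaluable participants (378 per arm). The stated result: "it was estimated that 400 participants per arm (800 participants in total) are required to provide 90% power".

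**Reproducing the plan's figure.** Per-participant variance of the log rate ratio:

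V = (1/1.7 + 0.55) + (1/1.309 + 0.55) = 0.5882 + 0.7639 + 1.10 = 2.452

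n per arm = (1.960 + 1.2816)² × V / (ln 0.77)² = 10.507 × 2.452 / 0.06831 = 377.2

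That is 378 per arm, or 756 in total, and 756 / (1 − 0.055) = 800. Power at 378 per arm is 90.06%. The 18 cells of Table 2 reproduce to within about 1 point. The sample size is sound.

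**Effect of the covariate, equal slopes.** If the log rate rises by b per unit of log eosinophils, with standard deviation SD, adjustment lowers k by about b² × SD² in each arm. The documents give neither b nor SD. Assumed: SD 0.35 to 0.45 (the 300 cells/µL entry rule narrows the range) and b 0.1 to 0.5.

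| SD | b | b²SD² | V after | Variance cut | Power at 1.7 | Power at 0.9 |
|---|---|---|---|---|---|---|
| none | none | 0 | 2.452 | 0 | 90.06% | 75.75% |
| 0.35 | 0.1 | 0.0012 | 2.450 | 0.1% | 90.09% | 75.78% |
| 0.45 | 0.5 | 0.0506 | 2.351 | 4.1% | 91.22% | 76.91% |

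As a share of 800 participants, the variance cut is worth about 1 to 33 people. A second parameterization (SD 0.3 to 0.5, rate ratio 1.1 to 1.3 per doubling of the count, residual k = 1.55/exp(b²SD²) − 1) gives 90.1% to 91.3% power at rate 1.7. Only the extreme corner, 1.5 per doubling with SD 0.5, reaches 92.9%.

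**Effect of the covariate, slope flat on mepolizumab.** With slope b on placebo and 0 on drug, a shared slope settles near b/2. The placebo dispersion then falls by b²SD² − b²SD²/4, while the drug dispersion rises by b²SD²/4. The net fall in V is b²SD²/2, against 2b²SD² with equal slopes: one quarter. At b = 0.5 and SD = 0.45, V falls by 0.0253 to 2.427, a cut of 1.0%, and power is 90.35%, a gain of about 0.3 points.

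**The case against.** The strongest objection is that the gain may be close to nothing. The trial selects on eosinophils mainly because higher counts are expected to bring greater benefit (Protocol 2.1 and 4.2), which implies a flatter slope on drug and hence the quarter-size gain above. The risk statement in Protocol 2.1 is qualitative, concerns COPD in general, and shows no gradient among people already at 300 cells/µL or more on triple inhaled therapy. The SAP does not say whether k = 0.55 was already covariate-adjusted. The model already adjusts for prior exacerbations, FEV1, smoking and region, and low event rates are met by blinded re-estimation and longer follow-up. Adding a covariate is also itself a departure from the protocol's list.

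All of this limits the size, but none of it gives a reason to leave the term out. In these calculations the gain is small but not negative. Possible effect modification does not rule out a main effect: without the term, the estimate still averages over the same variation.

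A reader might infer three further faults that the documents do not support:
- **Prior exacerbations wasted.** Protocol 2.2 reports that "the single best predictor of exacerbations was previous exacerbations", and the protocol lists "number of exacerbations in previous year" without grouping, whereas the SAP uses ≤2, 3, ≥4. But the history is in the model. One severe event qualifies for entry as two moderate ones do (Protocol 5.1), so pooling 1 with 2 is defensible, and the cap limits outlying counts. Recoding is a trade-off.
- **An undeclared change from the protocol.** Protocol 9.4.1 leaves full details of the methods to the analysis plan, so the coding is delegated detail.
- **The same change for time to first exacerbation.** SAP 4.3.1.2 has its own covariate list, and the Cox hazard ratio is non-collapsible: adding a prognostic covariate changes what is estimated.

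**Conclusion.** The point holds as a minor efficiency suggestion. The primary model omits a pre-randomization covariate that the trial collects on essentially everyone, that the protocol associates with risk, and that the SAP models elsewhere. The gain is about 0 to 1.2 power points at a placebo rate of 1.7 if the slope is common to both arms, and at most about 0.3 if it is flat on mepolizumab. Both ranges rest on assumed slopes and spread, since the documents give none. Adjustment for chance imbalance in the population-defining marker is a second, modest benefit.

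A reader might infer that the present model is biased or the trial undersized. Neither follows: the prespecified model has no bias or type I error problem on this account, and the figures of 756 and 800 reproduce.

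**What to change.** Before unblinding:
1. In SAP 4.2.2, add the log screening (Visit 0) eosinophil count, as defined in SAP 4.1.2, as a continuous main-effect covariate.
2. Carry it into the rate models that refer to 4.2.2, namely 4.3.5.2 and 4.4.2.2.
3. List the addition in SAP Table 1, since it extends the covariate list in Protocol 9.4.1.
4. Keep the interaction model in 4.2.5 exploratory.

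If unblinding has already taken place, leave the primary model as prespecified and report the eosinophil-adjusted model as a supplementary analysis only.

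The cost is SAP wording and programming, with no new data. Because the Visit 0 count is mandatory and has a fallback, the rule excluding participants with missing covariates should remove almost nobody.
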